3.4 Efficacy Assessment

Efficacy data will be summarized by randomized treatment based on the FA Population. The primary efficacy endpoint will also be summarized based on the mFA Population.

3.4.1 *Primary Endpoints Analysis*

The primary objective of the study is to determine whether the combination of SL BUP/NAL SOC background therapy and the digital therapeutic OXD01 is superior to SL BUP/NAL alone to reduce opioid use, as measured by the treatment success rate. Treatment success is defined as the subject having $\geq 80\%$ of urine drug tests negative for opioids plus $\geq 80\%$ of self-reports negative for illicit opioid use (from the TLFB interview at the same visit) from Week 6 to Week 25. Each subject will be evaluated as a success or failure for this metric and the proportion of subjects in each group demonstrating $\geq 80\%$ of urine drug tests negative for opioids plus negative self-reports for illicit opioid use (from the TLFB interview) will be tested using chi-squared test. Count and percentage of the subjects with treatment success will be summarized by treatment based on FA Population.

If the subject withdrew the study, then the urine drug tests for opioids and self-reports for illicit opioid use after withdrawal will be imputed as positive. If the subject completed the study with any missing visit, then the urine drug tests for opioids and self-reports for illicit opioid use for the missing visit will be imputed as positive.

Sensitivity analysis 1

As supportive analyses to the primary analysis for the primary endpoint, sub-group analysis using a similar chi-squared test as described above will be repeated for the following factors:

- Percentage of subjects meeting primary endpoint by reported compliance rate or who achieved greater than 80% completion of the visits during Week 6 to Week 25
- Subjects who took the dose of buprenorphine versus retention.
 - Target dose or lower: ≤ 16 mg buprenorphine for Suboxone or equivalent formulation; or ≤ 11.4 mg Zubsolv
 - Higher dose than target dose: > 16 mg buprenorphine for Suboxone or equivalent formulation; or > 11.4 mg Zubsolv
- Subjects who received additional behavioral health services

Sensitivity analysis 2

As supportive analyses, the primary endpoint and key secondary endpoints will be performed using the similar statistical methods based on mFA Population.

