## **6.9 Drug Screen**

A urine sample will be taken at screening, study Day 1, and at weekly visits during the study to test for the following drugs of abuse: amphetamines, barbiturates, benzodiazepines, cocaine metabolite, marijuana metabolite, methadone, opiates, phencyclidine, propoxyphene, and buprenorphine.

Precautions should be taken to prevent manipulation of the urine sample by the subject.

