2.2.4 Sample Size Determination

Treatment success is defined as the subject having $\geq 80\%$ of urine drug tests negative for opioids plus $\geq 80\%$ of self-reports negative for illicit opioid use (from the TLFB interview at the same visit) from Week 6 to Week 25 of the study. Current literature suggests that the proportion of subjects likely to be successful by this measure while under treatment with the control agent may be approximately 12%. [1] If OXD01 is effective in improving this percentage to 25%, approximately 200 subjects will be required to receive each treatment to provide 90% power to

detect such a difference at an $\alpha = 0.05$ level (Fisher's Exact Test). Approximately 510 opioid dependent males and females will be screened to randomize approximately 400 subjects.

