3.1.3 Definition of Baseline

Baseline is defined as Study Day 1. Subject with missing baseline value will be considered as missing and will be excluded from the analysis for the change from baseline endpoints.

3.1.4 *Summary Statistics*

In general, categorical data will generally be summarized with counts and percentages of subjects. The denominator used for the percentage calculation will be clearly defined.

Continuous data will generally be summarized with descriptive statistics including n (number of observations), mean, median, standard deviation, minimum, and maximum.

3.1.5 *Hypothesis Testing*

Corresponding with the primary efficacy objective of the study, the primary inference for hypothesis testing is the treatment difference between the combination of SL BUP/NAL SOC background therapy and the digital therapeutic OXD01, and SL BUP/NAL alone to reduce opioid use, as measured by the treatment success rate from Week 6 to Week 25. The hypothesis testing is based on a two-sided test with significance level at 0.05.

3.1.6 *Evaluation of Site Effect*

This is a multicenter study. Sites will not be pooled for any planned inferential analysis.

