3.3 Subject Data and Study Conduct

3.3.1 *Subject Disposition*

Counts and percentages of subjects who were randomized, discontinued early from the study, and completed the study will be summarized by treatment on all randomized subjects (FA Population). Reasons for early discontinuation will also be summarized.

For subjects that discontinued early from study, treatment success by treatment group will be investigated with a Kaplan-Meier survival plot, censored to when the subjects dropped out over the course of the study.

3.3.2 *Protocol Deviations*

Protocol deviations will be identified based on the clinical protocol as described in the Protocol Deviation Plan to align with ISO 14155:2020 (Clinical investigation of medical devices for human subjects – Good Clinical Practice). Protocol deviations will be identified prior to unblinding the database.

Counts and percentages of subjects with major protocol deviations by deviation category will be summarized by treatment based on FA Population.

3.3.3 *Analysis Populations*

Counts and percentages of subjects will be summarized by treatment based on FA Population.

3.3.4 *Demographic and Baseline Characteristics*

The following demographic and baseline characteristics will be summarized:

- Age (years)
- Sex
- Childbearing potential
- Race
- Ethnicity
- Baseline craving Visual Analog Scale (VAS)

Demographic and baseline characteristics will be summarized with descriptive statistics or counts and percentages of subjects as appropriate by treatment based on FA Population.

3.3.5 *Opioid Use History/ Treatment*

A treatment history, including counseling, over the previous 2 years for OUD will be recorded at screening. Opioid use history and treatment including main drug of abuse and primary route used, will be summarized by treatment based on Safety Population.

3.3.6 *Medical History*

Medical history will be coded to system organ class and preferred term using the Medical Dictionary for Regulatory Activities (MedDRA) version 24.0. Counts and percentages of subjects with medical history by system organ class and preferred term will be summarized by treatment based on the Safety Population.

3.3.7 *Concomitant Medications*

Concomitant medications that are ongoing on study Day 1 will be recorded. Additions, deletions, or changes to concomitant medications after Day 1 will not be recorded.

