APPENDIX B: SAS Programming Example

The sample SAS code for Chi-Squared test is included below:

```
PROC FREQ DATA=DATA;  
  TABLES RESPONSE * TREATMENT / CHISQ;  
  RUN;
```

The sample SAS code for Kolmogorov-Smirnov (KS) test is included below:

```
PROC NPAR1WAY DATA=DATA WILCOXON EDF;  
  CLASS TREATMENT;  
  VAR CUMULATIVE_RESPONSE;  
  RUN;
```

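### The primary chi-squared test is valid and adequately powered, but it leaves unused the Day 1 urine result already collected, a modest efficiency gain at almost no cost

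*SAP*

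**What the plan says.** SAP 3.4.1 and Protocol 11.3 classify each subject as a success or failure. The two proportions "will be tested using chi-squared test". The sample code in SAP Appendix B is "TABLES RESPONSE * TREATMENT / CHISQ", so only response and treatment enter. SAP 3.1.5 sets the level: "The hypothesis testing is based on a two-sided test with significance level at 0.05". For the primary endpoint the SAP plans counts, percentages and a test. It names no risk difference or confidence interval.

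Randomisation is described only as 1:1 (Protocol 6.13, SAP 2.2.2). Sensitivity analysis 1 in SAP 3.4.1 repeats the test by compliance or visit completion, buprenorphine dose and additional behavioral services, none of which is specified as a pre-randomisation value. Sensitivity analysis 2 repeats the methods in the mFA Population.

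Baseline data are available. Protocol 6.9 says: "A urine sample will be taken at screening, study Day 1, and at weekly visits during the study". TLFB (6.11) and craving VAS (6.14) are also taken on Day 1. The baseline table in SAP 3.3.4 includes craving VAS but not the Day 1 urine result, and SAP 3.5.2 provides only individual listings for the Week 1 to Week 5 dipstick.

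**The concern.** The endpoint is built from urine tests and self-reports between Weeks 6 and 25. Both are also measured on Day 1, and it is reasonable to expect that a subject already opioid-negative then is more likely to succeed. The screening result cannot serve, because inclusion criterion 5 requires it to be positive. The Day 1 result can vary, because it follows an induction of up to 14 days.

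If Day 1 status is prognostic, an analysis that ignores it is noisier than it needs to be. An imbalance between arms in that variable would be neither controlled by design, nor adjusted for, nor shown in a summary table. What is at stake is precision on the primary comparison. Under SAP 3.4.2 the secondary endpoints are tested in a gated sequence, so power matters in the first tests.

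**Working it through.** **Inputs from SAP 2.2.4.** The control success rate "while under treatment with the control agent may be approximately 12" per cent. The planned effect: "If OXD01 is effective in improving this percentage to 25" per cent. The size: "approximately 200 subjects will be required to receive each treatment to provide 90% power to" detect that difference.

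**1. The plan's own figure.** With d = 0.13 and mean rate 0.185, the two-sided formula is n = [1.96·√(2·0.185·0.815) + 1.2816·√(0.12·0.88 + 0.25·0.75)]² / d² = (1.076 + 0.694)² / 0.0169 ≈ 186 per arm, or 201 with continuity correction. Exact enumeration at 200 per arm gives 90.4% power for Fisher's exact test (the test named in SAP 2.2.4) and 92.6% for chi-squared. The stated 200 at 90% therefore reproduces, and the planned test exceeds it. Exact type I error of the chi-squared at a 12% rate is 4.9%.

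**2. Unadjusted precision.** SE = √[(0.1056 + 0.1875)/200] = 3.83 points. Power (unpooled normal) = Φ(0.13/0.0383 − 1.96) = 92.4%.

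**3. Precision with one binary baseline covariate.** The documents give neither Day 1 positivity nor its predictive strength, so both are assumed. With n per arm, per-stratum rates p and stratum-specific differences τ:

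V = (1/n)[E p_C(1−p_C) + E p_T(1−p_T)] + Var(τ)/(2n).

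Example: 50% Day 1 positive, odds ratio 5 for success (negative versus positive), overall rates held at 12% and 25%.
- Stratum rates, positive/negative: control 4.6%/19.4%, OXD01 11.2%/38.8%.
- Within-stratum variances: 0.1001 + 0.1686 = 0.2687.
- Var(τ)/2 = 0.25·(0.1936 − 0.0664)²/2 = 0.0020.
- nV = 0.2707 against 0.2931, a reduction of 7.6%. Power = Φ(0.13/0.0368 − 1.96) = 94.2%.

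For 50-80% positive, the reduction is 1.4-1.7% at odds ratio 2, 3.8-4.3% at 3, 7.6-9.4% at 5 and 13-18% at 10. This is equivalent to about 406 to 489 unadjusted subjects in place of 400.

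**4. Simulated power, CMH minus chi-squared, in percentage points** (200 per arm, 12% vs 25%, 400,000 trials per cell):

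| Day 1 positive | OR 1 | OR 2 | OR 3 | OR 5 | OR 10 |
|---|---|---|---|---|---|
| 10% | −0.2 | −0.1 | 0.0 | +0.2 | +0.3 |
| 50% | −0.2 | +0.2 | +0.7 | +1.6 | +2.7 |
| 70% | −0.2 | +0.2 | +0.8 | +1.9 | +3.7 |
| 80% | −0.2 | +0.1 | +0.7 | +1.8 | +3.7 |

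Under the null at 12%, both tests reject in about 5% of trials.

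**5. Chance imbalance.** Shift = average success gap between Day 1 groups × SD of the between-arm difference in prevalence, where SD = √(2q(1−q)/200). In the example: gap (14.8 + 27.5)/2 = 21.2 points, SD 5.0 points, shift 1.1 points. For 50-80% positive the one-SD shift runs from about 0.5 (odds ratio 2) to 1.6 points (odds ratio 10), which is 0.5/3.83 = 0.13 to 1.6/3.83 = 0.42 of a standard error. At 10% positive it is about half a point or less.

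**6. A smaller true effect.** At 12% vs 22%, SE = √[(0.1056 + 0.1716)/200] = 3.72 points and unadjusted power is 76.6%. Variance reductions of 4%, 8.5% and 15% would give 78.3%, 80.2% and 83.0%.

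**The case against.** The case for leaving the test alone is substantial. Chi-squared is the protocol's own prespecified test, it holds its level, and it exceeds the planned power. A reader might infer from the missing covariate that the primary result would be biased or the trial underpowered. The documents support neither. Randomisation leaves the unadjusted difference unbiased on average, and chance imbalance is already counted in its standard error, so adjustment reduces random error and does not remove a bias. Nor do the documents support a claim of a large gain: with a weak predictor, or few subjects positive, the gain is nil, and with no prognostic value CMH loses about 0.2 points.

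The covariate also needs work before use:
- SAP 3.5.2 describes a dipstick at screening and Weeks 1 to 5, separately from the UDS summarised for Weeks 6 to 25, while Protocol 6.9 describes one panel throughout. Whether Day 1 uses the endpoint's own assay is unsettled.
- The panel includes buprenorphine, which every subject is taking by Day 1, so opioid-positive needs a definition.
- The order of urine collection and randomisation on Day 1 is not stated, and Protocol 6.2 does not allow urine collection by telemedicine, so missing values are possible.

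Finally, the change departs from Protocol 11.3. The SAP already identifies 13 + 24 = 37 subjects with data reliability issues in an open-label trial, so a late change of primary test must be visibly independent of outcomes.

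All of this stands. It limits the size of the claim and adds conditions to the fix. It does not show that ignoring the collected baseline result is preferable: the possible loss is a few tenths of a point and the possible gain several points.

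**Conclusion.** The point holds as a free improvement that should be made, not as a defect in the test. The facts are clear from the documents: an unadjusted primary test, no described stratification, no baseline-adjusted analysis, and suitable Day 1 data. The size is uncertain because it rests wholly on assumed positivity (10-80%) and an assumed odds ratio (1 to 10). Within those ranges the power change is about −0.2 to +3.7 points, and about 0 to +0.8 for a moderate predictor (odds ratio 2 to 3). The benefit would be greater if the true effect is below the planned 13 points. The primary conclusion does not depend on this change.

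**What to change.** Make the change before database lock and without reference to outcomes by arm.

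1. In SAP 3.4.1 name one primary analysis: a Cochran-Mantel-Haenszel test stratified by Day 1 opioid urine result, with a Mantel-Haenszel risk difference and 95% CI. Keep the unadjusted chi-squared as supportive. Do not leave a logistic model with further covariates open as an alternative primary analysis, since it is a different analysis.
2. Define Day 1 opioid-positive by the same written rule that the endpoint uses for an opioid-positive test, with prescribed buprenorphine not counted.
3. Confirm that the Day 1 sample precedes allocation, and place missing Day 1 results in a fixed category.
4. Reconcile the dipstick wording in SAP 3.5.2 with Protocol 6.9.
5. Add the Day 1 urine result to the baseline table in SAP 3.3.4.
6. Record the change and its reason in SAP section 6, which now states that there is no deviation from the protocol analysis.

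The cost is a few sentences in the SAP, a stratum variable and the CMH and risk-difference output in the Appendix B code, and a documented departure from Protocol 11.3. No new data, subjects or visits are needed.

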- Proportion of subjects completing the study - A completer is defined as a participant who completed either the UDS or the self-report assessment at the Week 25 visit. The groups will be compared with respect to the proportion of completers using a chi-squared test.
- Clinical global impression - This will be evaluated in two ways
 - Score on the CGI-I scale at week 13 and Week 25
 - Change from baseline in the Clinical Global Impression-Severity score at Week 13 and Week 25

CGI scores will be evaluated using General Linear Model (GLM) methodology with treatment as categorical covariate. If substantial deviations from the model assumptions are observed, then supportive analyses such as non-parametric assessments including a Mann-Whitney U test will be performed.

- Opioid cravings - Change from baseline in the opioid craving score using the Opioid Craving VAS from Week 4 to Week 25. Opioid Craving scores will be evaluated using GLM methodology with treatment as categorical covariate. If substantial deviations from the model assumptions are observed, then supportive analyses such as non-parametric assessments including a Mann-Whitney U test will be performed.
- Use of illicit non-opioid drugs of abuse - The cumulative percentage of subjects with urine drug tests negative for illicit drugs of abuse (excluding opioids) plus self-reports negative for illicit drug use for the period from Week 6 to Week 25 will be evaluated using the Kolmogorov-Smirnoff methodology.
- Number of hospitalizations, emergency department visits, and overdoses, and the ability to resume work, school, or other productive activity. descriptive statistics (count and percentage) will be summarized by treatment.

3.4.3 *Exploratory Analysis*

- Percentage of subjects with longer abstinent – Longer abstinence is defined as a subject having urine drug tests negative for opioids as well as self-reports negative for illicit use of opioids at Week 22 – Week 25. Each subject will be scored as abstinent or non-abstinent and the groups will be compared using a chi-squared test.

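### The buprenorphine-dose subgroup analysis relies on separate chi-squared tests with no interaction test, so it cannot show whether the OXD01 effect differs by dose, and its dose bullet leaves the outcome unclear

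*SAP*

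**What the plan says.** SAP 3.4.1 compares treatment success between arms with a chi-squared test. Under Sensitivity analysis 1 it adds that "sub-group analysis using a similar chi-squared test as described above will be repeated for the following factors", and presents this as support for the primary analysis of the primary endpoint. The factors are compliance or visit completion, buprenorphine dose, and additional behavioral health services. The dose factor has two levels (target dose or lower, and higher than target) and is introduced as "Subjects who took the dose of buprenorphine versus retention". No time point is given at which dose is classified.

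The only significance level in the SAP is in 3.1.5, in a paragraph about the primary inference: "The hypothesis testing is based on a two-sided test with significance level at 0.05". No level, decision rule or multiplicity statement is written for the subgroup tests. The testing hierarchy in SAP 3.4.2 covers the secondary endpoints only. No interaction test appears in either document.

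SAP 3.4.3 (Exploratory Analysis) holds a single item, "Percentage of subjects with longer abstinent". SAP section 6 lists two additions to the protocol: that item and the modified full analysis population. Protocol 11.3 and 11.4 contain no subgroup analysis, so the subgroup tests are also an addition, and section 6 does not list them.

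**The concern.** A sensitivity analysis asks whether the same estimate survives different assumptions. A subgroup analysis by dose is naturally read as asking whether the effect varies with dose, and two separate p-values do not answer that. Each stratum has fewer subjects than the trial, so a uniform effect will often reach significance in one stratum and miss it in the other.

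The trial is meant to establish what OXD01 adds to buprenorphine/naloxone. Output with one significant and one non-significant dose stratum invites the conclusion that OXD01 works at one dose level only, when the data may show nothing of the kind.

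There is also a specification problem. The lead-in says the primary test is repeated, while the dose bullet names retention. A programmer cannot tell which outcome is to be compared, or between which groups.

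**Working it through.** **Inputs.** SAP 2.2.4 gives control success 12%, OXD01 success 25%, and says that "approximately 200 subjects will be required to receive each treatment to provide 90% power to" detect the difference, with "Fisher's Exact Test" named as the test. Alpha is two-sided 0.05 (SAP 3.1.5). Stratum sizes are not in the documents. I assume splits from 50/50 to 90/10 of 200 per arm, the same in both arms. I take the lead-in's reading: treatment success compared between arms within each dose stratum.

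**The plan's figure.** Exact two-sided Fisher power at 200 per arm is 90.4%, which reproduces the stated 90%. The chi-squared test gives 92.6% (exact).

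**Power within a stratum of n per arm.** With difference d = 0.13 and mean rate 0.185:

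- power = Φ((d√n − 1.96·√(2·0.185·0.815)) / √(0.12·0.88 + 0.25·0.75)) = Φ((0.13√n − 1.076) / 0.541)
- n = 200: Φ((1.838 − 1.076)/0.541) = 92.0%
- n = 100: Φ((1.300 − 1.076)/0.541) = 66.0%

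**Chance that exactly one stratum is significant under a uniform effect.** This is pA(1 − pB) + pB(1 − pA). At 50/50 it is 2 × 0.660 × 0.340 = 44.9%. Simulation with 400,000 trials per split checks this and adds two interaction tests: Wald on the log-odds scale (0.5 added to each cell) and on the risk-difference scale.

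| Split | n per arm | Stratum power | Exactly one: formula | Exactly one: simulated | Both: formula | Interaction, log-odds | Interaction, risk difference |
|---|---|---|---|---|---|---|---|
| 50/50 | 100 + 100 | 66% / 66% | 44.9% | 44.1% | 43.6% | 4.5% | 5.2% |
| 60/40 | 120 + 80 | 74% / 56% | 47.0% | 46.6% | 41.7% | 4.5% | 5.2% |
| 70/30 | 140 + 60 | 80% / 45% | 53.1% | 53.1% | 36.1% | 4.3% | 5.3% |
| 80/20 | 160 + 40 | 85% / 32% | 62.7% | 62.2% | 27.2% | 3.6% | 5.4% |
| 90/10 | 180 + 20 | 89% / 18% | 75.0% | 75.3% | 16.1% | 2.6% | 6.3% |

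Among simulated trials in which the overall test is itself significant, exactly one stratum is significant in 46% (50/50) to 80% (90/10).

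**No OXD01 effect.** At least one of two independent stratum tests is significant with probability 1 − 0.95² = 9.75% (simulated 9.3% to 10.5% at a 12% success rate). The overall test stays at 4.9% in the same simulations.

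**Power of the interaction test.** Suppose the whole effect sits in one stratum (12% against 25%) and the other has none (12% in both arms). The log odds ratio is ln[(0.25/0.75)/(0.12/0.88)] = 0.894. For 100 per arm the variances are 1/18.75 + 1/10.56 = 0.148 and 2/10.56 = 0.189.

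- 50/50: SE = √(0.148 + 0.189) = 0.581; power ≈ Φ(0.894/0.581 − 1.96) = 34%
- 80/20, effect in the larger stratum: SE = √(0.148/1.6 + 0.189/0.4) = 0.752; power ≈ Φ(0.894/0.752 − 1.96) = 22%

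**The case against.** A reader might infer that the dose tests double the trial's false-positive rate. The documents do not support that. The 9.75% applies only to the pair of stratum tests. They lie outside the primary test and outside the hierarchy in SAP 3.4.2, and no success claim is tied to them.

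A reader might also infer that each stratum is formally tested at 0.05 as an unlabelled confirmatory analysis. The 0.05 sentence concerns the primary inference, so its use for the subgroups is an inference. The analysis does have subordinate status, since it is called supportive. Nor can a family-wise rate over all three factors be derived: the compliance and behavioral-health bullets are not defined as two-level splits.

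Three further objections have force:

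- The dose bullet could mean one dose-by-retention table, with no treatment comparison in each stratum. The 44% to 75% would then not apply. This strengthens the case for defining the analysis.
- The SAP does not say that a dose difference will be concluded from two p-values. That is so, but it offers no other way to read them, and the misreading is a common one.
- SAP 3.4.1 classifies by the dose subjects took. Protocol 5.2 has dosing run from Day 1 to Day 169 as the investigator directs. If dose is classified after Day 1 in this open-label trial, treatment could influence stratum membership, and an interaction test would not remove that bias.

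**Conclusion.** The concern holds as a matter of interpretation and specification, not of confirmatory error control. As written, the dose analysis cannot show whether the OXD01 effect differs by dose. Under a uniform effect of the size planned, it would give one significant and one non-significant stratum in about 44% to 75% of trials. An interaction test on the log-odds scale would wrongly signal a difference in about 3% to 5% (5% to 6% on the risk-difference scale).

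These figures rest on 12% against 25%, 200 per arm, the assumed splits being equal in both arms, and treatment success being the outcome compared within strata. The direction is the same at every split tried. Independently of any arithmetic, the dose bullet contradicts its lead-in, and the classification time is missing.

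**What to change.** Before database lock, in SAP 3.4.1:

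- Name treatment success as the outcome of the dose subgroup analysis.
- Classify subjects by the dose recorded at Day 1, before any OXD01 exposure. If a later dose is used, label the strata post-randomization and descriptive only. Confirm where the dose is captured: Protocol 6.6 records medications ongoing on Day 1 and no later changes.
- Replace the stratum p-values with the success-rate difference and 95% confidence interval in each stratum, plus one treatment-by-dose interaction test, for example in a logistic model.
- Move the subgroup analyses to 3.4.3 as exploratory, state that no superiority claim will be made from a stratum, and list them in section 6.
- Tabulate retention by dose separately, or remove the reference to retention.

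The cost is wording and one model statement; if the Day 1 dose is already in the database, no new data are needed. The drawback is low power: about 22% to 34% even if the whole effect sat in one stratum. A non-significant interaction is therefore not evidence of a uniform effect, and the test must be read alongside the stratum estimates and intervals.

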### 5.3.2 *Assessment of Compliance*

Subjects must continue to use OXD01 for 15-30 minutes, 1-2 times per week from Day 1 (Section 5.3.1) through Day 169. Treatment compliance will be assessed through subject interviews at the following Visits: Weeks 2-5, 7, 9, 11, 13, 17, 21, and 25. Lapses in compliance with the recommended use of OXD01 will be addressed with the subject. The Investigator or designee will also record the following OXD01 usage information: typical number of sessions per week and duration of each session, and progress completing the chats since the previous evaluation. The Investigator or designee will reinforce the key concepts of recovery and working with OXD01 (OXD01 Clinician Guide, Maintaining Motivation and Monitoring Compliance).

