Concomitant medications will be coded to anatomical therapeutic chemical (ATC) class and preferred term using the WHO Drug Dictionary version March 2021G B3. For summary purposes, medications will be considered prior medications if they stopped prior to the first use of study device (Day 1) and concomitant medications if they were taken at any time after the first use of study device (i.e. started prior to Day 1 and were ongoing or started after Day 1).

If a medication has incomplete start or stop dates, dates will be imputed to determine whether a medication should be considered prior or concomitant. If a medication start date is incomplete, the first day of the month will be imputed for missing day and January will be imputed for

missing month. If a medication stop date is incomplete, the last day of the month will be imputed for missing day and December will be imputed for missing month. Incomplete start and stop dates will be listed as collected without imputation.

Counts and percentages of subjects taking concomitant medications by ATC class and a preferred term will be summarized by treatment based on the Safety Population.

3.3.8 *Study Device Compliance*

Dosing instructions will be reviewed and subjects will be interviewed to assess treatment compliance at the following Visits: Weeks 2-5, 7, 9, 11, 13, 17, 21, and 25.

Percent compliance of study device OXD01 will be calculated as the number of OXD01 sessions taken / the number of expected OXD01 sessions taken. Percent compliance to the study device regimen will be summarized based on the Safety Population with descriptive statistics and with counts and percentages of subjects with compliance in the following categories:

- <50%
- 50-80%
- 80-100%
- >100%

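### Sensitivity analysis 1 tests the arms within groups formed after randomisation, using a compliance rate that is loosely defined and exists only for OXD01, so its results can mislead in either direction

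*SAP*

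**What the plan says.** SAP 3.4.1 introduces Sensitivity analysis 1 with the words "As supportive analyses to the primary analysis for the primary endpoint" and states that "sub-group analysis using a similar chi-squared test as described above will be repeated for the following factors". The test described above it compares the randomised arms. Three of the listed factors matter here:

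- "Percentage of subjects meeting primary endpoint by reported compliance rate", with no cut-off and no rule for placing control subjects;
- visit attendance, worded "or who achieved greater than 80% completion of the visits during Week 6 to Week 25";
- receipt of additional behavioral health services.

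The list also has a buprenorphine dose factor, which this point does not address.

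The only compliance rate with a formula is in SAP 3.3.8: "Percent compliance of study device OXD01 will be calculated as the number of OXD01 sessions taken / the number of expected OXD01 sessions taken". It is summarised on the Safety Population, in classes that include 50-80% and 80-100%. Protocol 5.3.2 sets the expected use, "Subjects must continue to use OXD01 for 15-30 minutes, 1-2 times per week", and says what sites record at the 11 evaluation visits: "typical number of sessions per week and duration of each session, and progress completing the chats since the previous evaluation". Compliance with the background medication is assessed by interview in both arms (Protocol 5.2.1), but no rate is defined for it.

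Under SAP 3.4.1, missing visits and visits after withdrawal are scored positive for both urine test and self-report.

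**The concern.** Device use, attendance and use of counselling are all observed after randomisation. Each may depend on prognosis, on the assigned treatment, or on both. A between-arm test inside groups formed this way no longer compares like with like, and its p-value does not have its nominal meaning.

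The compliance factor has two further problems. Controls have no OXD01 sessions, so a compliant OXD01 subset has no counterpart, and the SAP does not say what it would be compared with. The rate also leaves its denominator and the cut-off open, so both could be settled after results are known.

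Attendance has a different problem. It is close to being part of the outcome, because an unattended visit is counted as a positive one.

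These are the plan's only efficacy analyses by device use, and they are offered as support for the primary result. A reader of the study report could take a significant subset result as evidence that using the application works, or a null one as evidence that it does not.

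**Working it through.** **1. The plan's own figure.** Inputs from SAP 2.2.4 and 3.1.5: 12% v 25%, two-sided 0.05, 200 per arm, 90% power with Fisher's exact test. Exact enumeration gives 90.4% for Fisher's test and 92.6% for the uncorrected chi-squared test, so the stated figure reproduces. With 12% in both arms and all 200 v 200 compared as randomised, the chi-squared test rejects in 4.9% of trials, 2.5% in favour of OXD01. That is the benchmark.

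**2. The compliance rate.** Expected sessions over 24 weeks run from 24 × 1 = 24 to 24 × 2 = 48.

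| Reported use | Sessions | Rate if 24 expected | Rate if 48 expected |
|---|---|---|---|
| 1 per week | 24 | 100% | 50% |
| 1.5 per week | 36 | 150% | 75% |
| 2 per week | 48 | 200% | 100% |

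Every row is within the instructed range, yet the class depends on an unstated choice. A subject at exactly 80% falls in two classes. The numerator can be approximated as typical sessions per week times weeks since the last evaluation, but it is self-reported and is not a count.

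**3. Compliers against all controls, no OXD01 effect.** This comparator is assumed, because the SAP names none. Let c be the complier share, with success p_C in compliers and p_N in the rest, so that c × p_C + (1 − c) × p_N = 12%. The test is z = (p_C − p_0) / √[p̄(1 − p̄)(1/n_C + 1/n_0)], where p_0 is control success, p̄ the pooled success proportion, n_C the number of compliers and n_0 = 200 controls at 12%. It rejects at |z| ≥ 1.96, with probabilities summed over all binomial outcomes. With c = 0.5, n_C = 100:

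| p_C / p_N (assumed) | Ratio | Trials with p<0.05 |
|---|---|---|
| 12% / 12% | 1 | 5.0% |
| 16% / 8% | 2 | 17.2% |
| 18% / 6% | 3 | 30.2% |
| 20% / 4% | 5 | 45.8% |

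For ratios above 1, nearly all of these favour OXD01. Over a wider grid (c from 0.3 to 0.7, ratio 1.5 to 3), the chance of a false result favouring OXD01 runs from 5.7% to 51.9%, against 2.5% as randomised.

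**4. Visit completion.** Weeks 6 to 25 give 20 weekly visits. Success needs 0.80 × 20 = 16 negative visits, so at least 16 attended; the subset needs more than 16, so at least 17. A subject outside the subset can succeed only by attending exactly 16 visits, all negative.

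Take 12% success in both arms (24 of 200 each) and assume all successes fall in the subset:

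| Attendance, control / OXD01 (assumed) | Subset success, control v OXD01 | p<0.05 | Of which favouring OXD01 |
|---|---|---|---|
| 50% / 50% | 24/100 = 24% v 24/100 = 24% | 5.0% | 2.5% |
| 50% / 40% | 24/100 = 24% v 24/80 = 30% | 14.5% | 14.3% |
| 50% / 60% | 24/100 = 24% v 24/120 = 20% | 11.4% | 0.4% |

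The reverse case is a benefit that works through retention. If OXD01 raises completion from 30% to 40% and 40% of attenders succeed in each arm, true success is 0.30 × 40% = 12% v 0.40 × 40% = 16%, but the subset shows 40% v 40%.

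**5. Behavioral services.** The documents give no figures. Protocol 6.16 records participation during treatment, so the same reasoning applies without a size.

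**The case against.** The best defence is that these analyses are labelled supportive, the primary test uses all randomised subjects, and the compliance line may mean no more than tabulating success by compliance category. The inflation figures depend on a complier share and a prognostic ratio that the documents do not give.

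Most of that stands. The primary type I error is untouched. If compliance is unrelated to prognosis there is no inflation, and the visit-completion test holds its 5% level if OXD01 affects neither attendance nor outcome. But the tabulation reading sits badly with a lead-in that calls for the chi-squared test to be repeated, and it does not rescue the visit-completion and behavioral-services factors, which exist in both arms and are formed after randomisation.

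A reader might infer three stronger things that the documents do not support:

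- That the SAP plans to set compliant OXD01 users against all controls. It never says so; the comparator is simply missing.
- That the compliance rate cannot be calculated from the collected data. The interviews do give an approximate numerator; the gap is a fixed denominator and an exact count.
- That these analyses must favour OXD01. Step 4 shows bias against it when OXD01 improves attendance.

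**Conclusion.** The point holds for the supportive analyses and should be corrected, but it does not threaten the primary result. Sensitivity analysis 1 prescribes between-arm tests by post-randomisation factors, one of which has no defined value in controls and another of which overlaps the endpoint. With no true effect, a complier-against-all-controls test would reject in about 17-46% of trials under the assumed 16-20% v 8-4% success and a 50% complier share. The attendance subset would falsely favour OXD01 in about 14% of trials under the assumed 40% v 50% attendance, and would work against OXD01 if attendance were higher in its arm. These sizes are illustrations. What follows from the documents alone is the structure of the problem and the factor-of-two ambiguity in the compliance denominator.

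**What to change.** In SAP 3.4.1, remove the between-arm chi-squared tests by compliance, visit completion and behavioral services. Report success by compliance category descriptively within the OXD01 arm, and success by attendance and by behavioral services descriptively by arm, with every table labelled as a non-randomised comparison. Address attendance through missing-data sensitivity analyses in all randomised subjects.

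In SAP 3.3.8, settle the following before treatment assignments are released for analysis:

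- one numerator source: typical sessions per week times weeks since the last evaluation, or platform records if they can be retrieved (the documents do not say);
- one expected-session denominator, with a rule for early withdrawal. Without such a rule, a once-weekly user who leaves at Week 12 (Day 78, 11 weeks) scores 11/24 = 46% against a fixed 24 sessions and is already a failure, so dropout becomes non-compliance;
- non-overlapping classes, summarised in the OXD01 arm only.

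A complier average causal effect is optional. It needs a prespecified use threshold and the stated assumption that assignment has no effect below it. That assumption matters. If 50% of the arm gained 15 points, 30% gained 7.5 and 20% gained none, the overall difference would be 0.5 × 15 + 0.3 × 7.5 = 9.75 points, and 9.75 / 0.5 = 19.5 would overstate the 15.

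The cost is mainly SAP wording, plus the missing-data analyses and a platform export if that source is chosen. The downside is that these subsets will carry no formal p-values.
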